6.2.4 Followup Visits

The following study visits must be performed on the weeks indicated above in the Schedule of Evaluations (please see Section 6.1) plus/minus 5 (five) *working* days (i.e., Monday through Friday, not including weekends and holidays):

- Visit 1:
 - Informed Consent Form
 - Medical History Form
 - Inclusion/Exclusion criteria form
 - Enrollment/Randomization form
 - MRI Screening Form & urine pregnancy test
 - MRI brain scan
 - Demographics assessment (electronically in Qualtrics)
 - SDQ assessment (electronically in Qualtrics)
 - Baseline Checklist
- Visit 2 through Visit 13:
 - Child Session Rating Scale (CSRS)
 - Child Outcome Rating Scale (CORS) including the question: "Has there been any significant unfavorable change in your mental or physical health since last class?" (please see Appendix. Not a source document.)
 - Adverse Events (if answered Yes the question above in CORS)
 - Serious Adverse Events (if answered Yes to the SAE question in the Adverse Event form)
 - On Study Visit Checklist Form (modified to include Treatment Administration information)

6.2.5 Completion/Final Evaluation.

The following assessments will be performed at the participant's final visit (Visit 14):

- SDQ assessment (electronically in Qualtrics)
- MRI Screening Form & urine pregnancy test
- MRI brain scan
- Child Outcome Rating Scale (CORS) including the question: "Has there been any significant unfavorable change in your mental or physical health since last class?" (please see Appendix. Not a source document.)
- Adverse Events (if answered Yes the question above in CORS)
- Serious Adverse Events (if answered Yes to the SAE question in the Adverse Event form)
- Study Completion form.

For study participants who discontinue the study intervention early, all of the following assessments will be performed:

- SDQ assessment (electronically in Qualtrics)
- MRI Screening Form & urine pregnancy test
- MRI brain scan
- Child Outcome Rating Scale (CORS) including the following question: "Has there been any significant unfavorable change in your mental or physical health since last class?" (please see Appendix. Not a source document.)
- Adverse Events (if answered Yes the questions above in CORS)
- Serious Adverse Events (if answered Yes to the SAE question in the Adverse Event form)
- Study Completion form.

Potential reasons for early terminations: (1) participant moves away to a distant part of the country or another country outside of the United States, (2) participant is involved in a severe motor vehicle accident that precludes the participant from being able to continue on with the study, (3) participant is involved in a plane crash that results in either death or severe disability that precludes the participant from further participation in the study, (4) participant is diagnosed with a severe illness that precludes them from being able to continue further with participation in the study.

Once a study participant has stopped using the study intervention, there are no specific requirements (e.g., related to monitoring and reporting of adverse events) for follow-up since the study intervention (i.e., TARA) is considered very minimal risk by our institution's IRB.

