6.2 Description of Evaluations

6.2.1 Screening Evaluation

These evaluations occur to determine if the candidate is eligible for the study.

Definitions of the column headings in the Schedule of Evaluations (Section 6.1): (1) Assessment refers to the specific assessments as listed in the first column that will be performed at each of the study visits; (2) Visit 1 (Day 0) refers to all of the assessments that will occur at the first study visit; (3) Visits 2 to 13 refer to the assessments that will occur at each of the study visits 2 through 13 which correspond to the TARA study intervention sessions 1 through 12 (i.e., Study Visit 2 is TARA study intervention session 1 since the first TARA study intervention session will take place on Study Visit 2); (4) Final Visit 14 refers to all of the assessments that will occur on the final study visit which will be Visit 14. Please note that in the above Schedule of Evaluations (Section 6.1), the AE and SAE forms only will be completed if an AE and/or SAE are reported by a participant. In addition, if a participant prematurely leaves the study, all of the assessments listed under the final study visit 14 column will be performed.

A phone pre-screening evaluation will occur to determine if the candidate adolescent is eligible for the study prior to the initial visit, and a screening evaluation will occur at Visit 1 (Day 0) to determine if the candidate is eligible to enter the study.

Consenting Procedure

A trained research staff member who will have at least a college degree (i.e., Bachelor's degree or higher) will perform the following informed consent process.

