7.3 Adverse Events and Serious Adverse Events

In the present study, an adverse event and serious adverse event will be defined as follows:

An adverse event (AE) will be defined as any unfavorable and unintended diagnosis, symptom, sign (including an abnormal laboratory finding), syndrome or disease which either occurs during the study, having been absent at baseline, or if present at baseline, appears to worsen. Adverse events will be recorded regardless of their relationship to the study intervention.

A **serious adverse event (SAE)** will be defined as any untoward medical occurrence that results in death, is life threatening, requires inpatient hospitalization or prolongation of existing hospitalization, results in persistent or significant disability/incapacity, or is a congenital anomaly.

Since we do not anticipate any laboratory value changes due to the TARA study intervention, no laboratory values will be collected as part of the current protocol; thus, no laboratory values will be collected to assess safety.

Solicited adverse events will be captured in the following manner: (1) the Child Outcome Rating Scale (CORS) including the following question: "Has there been any significant unfavorable change in your mental or physical health since last class?" will be administered at every TARA session (please see Appendix. Not a source document.); (2) if the participant answers "no" to this question on the CORS, then no additional information will be requested; (3) if the participant answers "yes" to this question on the CORS and the reported event meets the definition of an adverse event given above, then the research assistant or another study staff member will ask the participant for additional details regarding the participant's answer to the CORS question and this information will be recorded in the Adverse Event form within 24 hours of the TARA study intervention session.

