7.4 Reporting Procedures

Please see below, Table A, for details of the reporting procedures and timelines, including the individual responsible for each step (e.g., the PIs, the Independent Monitors, etc.). The medical director, [name] (co-PI), will make the decision regarding determining the relatedness and severity of any and all AEs and SAEs. The appropriate AE and SAE forms will be completed. The completed AE and SAE forms will be sent and distributed to the appropriate individual or group of individuals (i.e.,

UCSF IRB, NCCIH) as stated below in Table A (please see below, Table A). The PIs will record all reportable events with start dates occurring any time after informed consent is obtained until 7 days (for non-serious AEs) or 30 days (for SAEs) after the last day of study participation. A research assistant will perform the duties of the Internal QA reviewer. At each study visit, the investigator will inquire about the occurrence of AE/SAEs since the last visit. Events will be *followed* for outcome information until resolution or stabilization.

Table A

Data type	Frequency of review	Reviewer
Subject accrual (including compliance with protocol	Monthly	PIs, Internal QA Reviewer
enrollment criteria)	Semi-annually	Independent Monitors
Status of all enrolled subjects, as	Monthly	PIs, Internal QA Reviewer
of date of reporting	Semi-annually	Independent Monitors
Data entry quality control checks on 100% of charts	Weekly	QA Reviewer
Adherence data regarding study	Monthly	PIs, Internal QA Reviewer
visits and intervention	Semi-annually	Independent Monitors
AEs and rates (including out-of-	Monthly	PIs, Internal QA Reviewer
range lab values)	Semi-annually	Independent Monitors
	Annually	NCCIH
SAEs (unexpected and related)	Per occurrence	PIs, Independent Monitors NIH/NCCIH
SAEs (expected or unrelated)	Per Occurrence	PIs, Internal QA Reviewer
	Annually	Independent Monitors, NIH/NCCIH
Unanticipated Problems	Monthly	PIs, Internal QA Reviewer
	Per Policy	IRB

Reporting Changes in Study Status

During the funding of this study, any action by an IRB, the Independent Monitors, or one of the study investigators that results in a temporary or permanent suspension of the study will be reported to the NCCIH Program Official within 3 business days of notification.

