7.5 Followup for Adverse Events

The PIs will record all reportable events with start dates occurring any time after informed consent is obtained until 7 days (for non-serious AEs) or 30 days (for SAEs) after the last day of study participation. At each study visit, the investigator will inquire about the occurrence of AE/SAEs since the last visit. Events will be followed for outcome information until resolution or stabilization. In the cases of adolescents with severe depression or adolescents expressing passive suicidal ideation (i.e., the adolescent expresses some potential thoughts of self-harm, but there is no intent or plan to harm herself/himself), study participants with commercial or private health insurance plans will be referred to the UCSF Langley Porter Psychiatric Institute where [name] (co-PI) sees patients, and study participants without commercial or private insurance will be referred to the UCSF Zuckerberg San Francisco General Hospital which cares for all patients regardless of their ability to pay. Participants expressing imminent suicidal ideation will be placed on an involuntary 5150 72-hour hold for danger to self by [name]. [name] is a double board certified adult as well as child and adolescent psychiatrist who sees patients at UCSF, and he is legally authorized to place an involuntary 5150 72-hour hold on the adolescent for danger to self (i.e., suicidal ideation) in order to hospitalize the adolescent if needed. The UCSF Emergency Room (ER) is located immediately adjacent to the UCSF Langley Porter Psychiatric Institute where [name] personal clinical office and research lab are located. Following the established written protocols that are currently in place for any adolescent who expresses imminent suicidal ideation, [name] would evaluate and place an involuntary 5150 72-hour hold for danger to self on the suicidal adolescent. [name] would then contact the UCSF Langley Porter Psychiatric Institute security who are present in the building throughout the entire day and evening to help escort the suicidal adolescent to the UCSF ER. The ER physician in consultation with the on call child and adolescent psychiatrist would then evaluate the patient in the ER and decide whether to hospitalize the patient for the adolescent's safety and well-being.

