Emotional Problems. Our hypothesis is that training will improve emotional problems as assessed by the SDQ T-score compared with controls. We will use an analysis of covariance (ANCOVA) accounting for sex and fit by maximum likelihood. Stata (College Station, TX) will be used to perform data analyses. We will additionally explore age, pubertal status (as determined by the Tanner stage self-report form (Tanner et al., 1962)), and pre-training associations with the changes through an examination of interaction. Potential pre-/post-training differences in movement during MRI will be accounted for by assessing the number of rejected diffusion directions. Sex as a biological variable: In all analyses described, sex will be included as a factor, we will also test for a randomized arm by sex interaction.

In addition, we will examine relationship between changes in node strength of the putamen and changes in emotion by performing a Spearman rank correlation change in node strength through 12 weeks with change in SDQ through 12 weeks.

Other outcomes.

Adherence. We summarize adherence to training including (i) tabulating the number of participants on the training arm who complete at least 75% of sessions, (ii) calculate the minimum, maximum, median and interquartile range of sessions attended by those randomized to the TARA training arm.

Safety and tolerability of the intervention. Adverse events of grade 2 or higher will be tabulated between the arms and compared by the Fisher exact test. Tolerance scores on the CSRS will be summarized (minimum, maximum, median, interquartile range) at each study visiting on the TARA training arm.

We will tabulate the proportion of participants who are retained through 12 weeks and complete the MRI exam and SDQ questionnaire. These will be compared between the arms by the Fisher exact test.

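### The question that opens an adverse-event form looks back to the last class, while 7.4 and 7.5 look back to the last visit; read literally, it has no reference point for waitlist participants at Visit 14 or for TARA participants at their first class

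*Combined protocol and SAP*

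**What the plan says.** Two rules govern how an adverse event comes to be recorded.

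**The instrument.** Section 6.2.4 gives the safety item on the CORS for Visits 2 to 13: "Has there been any significant unfavorable change in your mental or physical health since last class". Section 6.2.5 repeats it for Visit 14 and for early discontinuation, and 7.3 and 10.1 use the same look-back. The AE form depends on the answer: the visit list reads "Adverse Events (if answered Yes the question above in CORS". After a negative answer, 7.3 states, "then no additional information will be requested". Section 7.3 also sends unsolicited reports back to the CORS, to be written after the same item.

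**The reporting sections.** Sections 7.4 and 7.5 say: "At each study visit, the investigator will inquire about the occurrence of AE/SAEs since the last visit". They also set a wider recording window: "The PIs will record all reportable events with start dates occurring any time after informed consent is obtained until 7 days" after the last day of participation, or 30 days for serious events.

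The AE and SAE rows in the 6.1 schedule do not amount to a further question. Section 6.2.1 explains that "the AE and SAE forms only will be completed if an AE and/or SAE are reported by a participant".

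The data feed a planned comparison in 9.6: "Adverse events of grade 2 or higher will be tabulated between the arms and compared by the Fisher exact test".

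**The concern.** The look-back in the item that triggers the form is shorter than the period that 7.4 and 7.5 say is covered, and the shortfall is not the same in the two arms. Visits 2 to 13 are defined in 6.2.1 as TARA sessions 1 to 12, and Section 3 says controls receive the intervention later. A control reaching Visit 14 has attended no class, so the item as worded names no period. A TARA participant at Visit 2 is in the same position for the time between randomization and the first class, but from then on each session supplies a reference point.

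Two things are at stake: whether events in adolescents are recorded at all during those periods, and whether the between-arm comparison in 9.6 counts events by the same rule in both arms. If controls answer the item literally, their events drop out and TARA looks less safe than it is.

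**Working it through.** **Step 1: the look-backs side by side.**

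| Situation | CORS item (6.2.4, 6.2.5, 7.3, 10.1) | Investigator inquiry (7.4, 7.5) |
|---|---|---|
| TARA, Visit 2 (first class) | no earlier class, so no period | since Visit 1; up to 4 weeks from randomization (6.2.2) |
| TARA, Visits 3 to 13 | since the preceding class | since the preceding visit (the same if all sessions are attended) |
| TARA, Visit 14 | since the final class | since Visit 13 (the same) |
| Waitlist, Visit 14 | no class attended, so no period | since Visit 1 |

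The waitlist interval is about 12 weeks on the outcome timing in 9.5.1 and 9.5.2, and up to about 20 weeks on the follow-up described in Section 3 (4 + 12 + 4). That controls have had no class by Visit 14 is an inference, because no separate waitlist schedule is given. It follows from Section 3 and 6.2.1.

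**Step 2: does anything carry out the 7.4/7.5 inquiry?** No row in 6.1 and no form in 10.1 does so. The AE form is conditional on the CORS answer, and 7.3 closes the questioning after a negative one. The two rules can therefore give different counts at the same visit.

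**Step 3: number of scheduled CORS safety items.** TARA: 12 sessions + Visit 14 = 13. Waitlist: Visit 14 only = 1. With 50 per arm and full attendance, 13 x 50 = 650 against 1 x 50 = 50.

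**Step 4: what differential capture could do to the Fisher test.** The plan gives no event rate and no capture figure, so there is none to reproduce. Inputs: 50 per arm (Section 3); an assumed true any-cause grade 2 or higher rate r, equal in both arms; assumed capture fractions c_T (TARA) and c_W (waitlist). An 80% TARA capture corresponds to 4 of 20 weeks uncovered at a constant event rate: 1 - 4/20 = 0.80. By exact enumeration,

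P(p < 0.05) = sum over a, b of Bin(a; 50, r x c_T) x Bin(b; 50, r x c_W) x 1{two-sided Fisher p(a, b) < 0.05}.

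| r | c_T | c_W | Recorded rates | P(p < 0.05) |
|---|---|---|---|---|
| 20% | 100% | 100% | 20% v 20% | 2.8% |
| 20% | 100% | 50% | 20% v 10% | 19.5% |
| 20% | 80% | 50% | 16% v 10% | 8.0% |
| 10% | 100% | 100% | 10% v 10% | 1.8% |
| 10% | 100% | 50% | 10% v 5% | 6.3% |
| 10% | 80% | 50% | 8% v 5% | 2.8% |
| 5% | 100% | 50% | 5% v 2.5% | 1.2% |
| 5% | 100% | 0% | 5% v 0% | 3.8% |

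With waitlist capture at 50%, rates of 10-20% give roughly 3-20%. At a 5% rate even zero waitlist capture stays below the nominal 5%.

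**The case against.** The strongest reply is that controls do have a defined period. Sections 7.4 and 7.5 promise an inquiry at each study visit, 9.5.2 says adverse events are collected at each visit, and for a control at Visit 14 the previous visit is Visit 1. A reader might infer from the CORS wording that the waitlist has no safety look-back at all; the documents do not support that. What stands is narrower: the promised inquiry has no form or schedule row, and 7.3 shuts the questioning after a negative CORS answer. Whether it takes place depends on which section staff follow.

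The CORS and AE forms are in an appendix that is not in the text reviewed, so their final wording for controls cannot be checked. The body of the protocol gives one wording and no alternative.

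It is tempting to quote larger figures. At a 20% true rate with full TARA capture, waitlist capture of 25% gives 51% and zero capture gives 95%. Those need a rate with no source in the documents, in adolescents screened as healthy; complete TARA capture despite the gap before the first class; and, for the 95%, every affected control answering no with the 7.4/7.5 inquiry never made. At 80% TARA capture the 51% falls to 29%. Nor do capture fractions separate the effect of wording from the effect of asking 13 times rather than once.

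A reader might also suppose that someone returning from an absence takes the last class to be the one missed. Nothing in Section 8 suggests that reading, and it forms no part of this point.

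**Conclusion.** The conflict is real and stands on the text alone: two look-backs are written for the same events, and the one that opens the form has no reference point for controls at Visit 14 or for TARA participants at Visit 2. The likely direction is under-recording of control events relative to TARA, which biases the 9.6 comparison against TARA. TARA's own gap before the first class partly offsets this. The size cannot be known from the documents; the 3-20% range rests wholly on the assumed rates and capture fractions in the working.

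The consequence is limited to completeness of safety records and that one comparison. A reader might infer that the trial's decisions are compromised, but they are not. The go/no-go criteria (1.1) rest on effect size and retention, and the 15% criterion and review trigger (7.1, 9.4, 9.5.2) count events related to TARA, so neither depends on waitlist events. The primary outcome and sample size are untouched. It should be corrected because the remedy is small.

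**What to change.** Replace the class-based look-back with one arm-neutral wording that matches 7.4 and 7.5: *since your last study visit*, with a standing note, identical for everyone, that this means Visit 1 if no class has been attended. Use it in 6.2.4, 6.2.5, 7.3 (including the text on unsolicited events), 10.1 and the CORS form.

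Do not have staff enter a participant-specific date of last contact. At Visit 14 that date would be Visit 1 for a control and the last session for a TARA participant, which could reveal allocation to assessors who are to stay blinded (5.2, 6.2.3).

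In 9.6, state that the between-arm table counts events with onset from randomization to Visit 14 in both arms, so that controls' later TARA sessions do not enter it.

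The cost is a minor IRB amendment and slightly more events recorded, mainly in controls and before the first class. The change does not remove the difference in scheduled questions, 13 against 1. The analysis section should acknowledge that difference when the comparison is interpreted.

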7. SAFETY ASSESSMENTS

Participant safety will be monitored once an individual is enrolled in the study. Since our institutional IRB has deemed our TARA intervention to be very minimal risk, we do not anticipate any significant adverse experiences from our TARA intervention. However, to assure comprehensive review of potential safety events, we have included the following alphabetical list of expected adverse experiences for the TARA study intervention, criteria for management and modification of the TARA study intervention regimen or participant assessments if an adverse event occurs:

- 1. Experiencing difficult emotions such as sadness or anger during some of the TARA intervention class activities or home assignments. If participants experience difficult emotions, they can stop the activity and speak to the class leader or study staff. The class leader will talk about how to handle difficult emotions that come up during home assignments at the first class, and throughout the course as needed.
- 2. Restlessness. If participants experience restlessness, they can stop the activity and speak to the class leader or study staff. The class leader will talk about how to handle restlessness that come up during home assignments at the first class, and throughout the course as needed.

If an adverse event occurs, the AE will be assessed by [name] (medical director and co-PI) and recorded in the Adverse Event form (please see Adverse Event form in the Appendix).

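### One sentence in Section 6.2.5 waives adverse event follow-up once TARA is stopped, contradicting Section 8 and inconsistent with Sections 7.4 and 7.5

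*Combined protocol and SAP*

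**What the plan says.** Section 6.2.5 (Completion/Final Evaluation) lists the assessments due when a participant discontinues the intervention early. They include the SDQ, the MRI, the CORS with its question on unfavourable health change, and the adverse event and serious adverse event forms where triggered. After some example reasons for early termination, the section closes by saying that once TARA has been stopped "there are no specific requirements (e.g., related to monitoring and reporting of adverse events) for follow-up since the study intervention" is regarded by the IRB as very minimal risk.

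The safety sections read differently. Section 7 opens with "Participant safety will be monitored once an individual is enrolled in the study". Section 7.3 adds "Adverse events will be recorded regardless of their relationship to the study intervention". Section 7.4 has the investigators record events that qualify as reportable, "with start dates occurring any time after informed consent is obtained until 7 days (for non-serious AEs) or 30 days (for SAEs"), these limits being counted from the end of study participation, and Section 7.5 repeats that window. Section 7.5 also states: "Events will be followed for outcome information until resolution or stabilization". Both sections have the investigator ask about events at each study visit.

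Section 8 (Intervention Discontinuation) requires one more visit with all Visit 14 assessments when TARA is discontinued. After that visit the participant is no longer followed, except for adverse events and serious adverse events under Section 7.4. It says this twice: for participants who no longer meet the entry criteria, and for permanent discontinuation generally.

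**The concern.** The same trigger, stopping TARA, leads to two opposite instructions on adverse events. Section 6.2.5 gives event monitoring and reporting as its example of what is not required. Section 8 gives event follow-up as the one thing that continues after the final visit.

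A staff member who relies on Section 6.2.5 alone could stop collecting new events, or stop following known ones to their outcome, when a participant leaves the classes. Adverse events feed the safety criterion in Section 7.1 (fewer than 15% of participants with a related grade 2 or 3 event), the safety-review trigger in Section 9.4 and the between-arm Fisher exact test in Section 9.6. A participant who stops TARA because of a related event is one whose follow-up matters to the first two.

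**Working it through.** No arithmetic applies. The documents give no count or rate of events after TARA is stopped, and the plan states no figure to reproduce. The check is a comparison of texts.

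1. **Trigger.** Section 6.2.5 applies once a participant has stopped the intervention. Section 8 applies when the intervention is discontinued for a participant. These are the same situation.

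2. **Rule after the trigger.**
   - Section 6.2.5, closing sentence: no specific follow-up requirement, with adverse event monitoring and reporting as the example.
   - Section 6.2.5, early-discontinuation list: CORS, and adverse event and serious adverse event forms where triggered.
   - Section 8: one further visit with all Visit 14 assessments, then event follow-up under Section 7.4.
   - Sections 7.4 and 7.5: events recorded if they start within 7 days (non-serious) or 30 days (serious) after participation ends, and followed until they resolve or stabilise.
   - Section 6.2.1: all Visit 14 assessments for anyone who leaves prematurely.

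   The first rule cannot be followed together with the rest. The conflict with Section 8 is direct. Section 6.2.5 also disagrees with itself.

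3. **Do the different clocks reconcile the texts?** Section 6.2.5 counts from stopping TARA, and Sections 7.4 and 7.5 count from the end of study participation. Taken alone, those two sections might therefore seem to govern a different period. They do not. A participant who stops TARA is still in the study until the Visit 14 assessments, so the 7-day and 30-day limits have not begun to run. Section 8 also expressly applies Section 7.4 to participants discontinued from TARA.

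4. **Does the stated reason reconcile them?** The reason given is TARA's very minimal risk. Section 7.3 has events recorded whatever their relationship to the intervention, so low intervention risk does not remove the duty. Section 7 repeats the minimal-risk view and still requires monitoring.

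**The case against.** The strongest reply is that this is one stray sentence which the rest of the protocol overrides. Section 8 is the dedicated section on stopping the intervention, Section 7.5 is the dedicated section on event follow-up, and Sections 6.2.1 and 6.2.5 both require final-visit assessments for early leavers. Since the stated reason is the risk of TARA, the sentence might also be meant only to say that TARA calls for no special post-exposure follow-up.

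The first part stands as a limit on the consequence: staff could be misled, but the documents do not show that they would be. The second part is strained, because the sentence names adverse event monitoring and reporting as its example and makes no reference to duties set elsewhere.

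A reader might infer two stronger points, and the documents support neither.

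- **That events causing a participant to leave would go unrecorded.** The sentence follows a list of early-termination reasons that includes "participant is diagnosed with a severe illness that precludes them from being able to continue further with participation in the study", and some of these could be serious under Section 7.3 ("any untoward medical occurrence that results in death, is life threatening, requires inpatient hospitalization or prolongation of existing hospitalization"). But an event that causes the stop begins before or at the stop, inside the Section 7.4 recording window. The sentence speaks of follow-up after stopping; it does not cancel recording of what has already happened. For such events, mainly follow-up to outcome is exposed.
- **That capture at the final visit rests only on the participant's answer to the CORS question.** Sections 7.4 and 7.5 separately have the investigator ask about events at each visit, and Section 7.3 provides a route for unsolicited reports to staff.

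**Conclusion.** The point holds as a minor error in a safety instruction. The closing sentence of Section 6.2.5 contradicts Section 8 directly and is inconsistent with Sections 7.4 and 7.5 and with the early-discontinuation list in its own section. What is at risk is collection of new events after TARA is stopped and follow-up of existing ones, and only where staff act on that sentence alone.

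The size cannot be put as a number. The rules affected are the 7-day and 30-day onset windows and follow-up until events resolve or stabilise. No sample size, primary analysis or secondary analysis depends on the sentence. The conclusion assumes that Sections 7.4, 7.5 and 8 state the intended rule, which is the natural reading because they are the dedicated safety and discontinuation sections and agree that event follow-up continues.

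**What to change.** Delete the closing sentence of Section 6.2.5, or replace it with: *After a participant stops TARA, adverse events are recorded and followed as in Sections 7.4, 7.5 and 8.*

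The cost is a one-sentence wording amendment, with no new visit, form or analysis. The change removes a contrary instruction but does not add active event collection: the schedule in Section 6.1 still shows no contact after Visit 14.
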